#### Saliva Sample Collection:

Saliva will be collected from enrolled infants and parents non-invasively to evaluate the effects of KFC on established biomarkers of stress (cortisol and testosterone) and father-infant bonding (oxytocin). Before, during, and after each KC session, saliva will be collected from the participating parent, and their infant. A trained member of the study team will collect saliva from the infant using suction, a method that follows the standard of care for the infant, or oral swabs (27) made from an inert polymer and appropriately sized for an infant mouth (approximately 5 mm). Saliva samples will be taken from the infant immediately prior to beginning a KC session (T1), 30 minutes into the KC session (T2), and 30 minutes post-session (T3). Parents will self-collect saliva samples at the time points outlined above, using an adult-sized oral swab. At T2, the trained study team member will be able to help the parent collect the saliva sample, if necessary, while the parent continues to hold their infant. This approach to salivary sample collection and biomarker analysis is similar to that established by previous studies of kangaroo care (26,27) and takes into consideration the 30-minute delay before cortisol reactivity in saliva.

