## 4.2. Discontinuation Criteria

A participant may be discontinued if the participant is unwilling or unable to tolerate the wearable sensors, saliva collection, or skin-to-skin session. Examples may include adverse reactions to the adhesive on the wearable sensors or a patient removing the wearable sensors. The bedside clinical team or family can also request discontinuation at any time. Families participating in the video monitoring can request discontinuation of the video monitoring aspect of this study at any time during the study.

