# 4.3. Patient Withdrawal

Any participants withdrawn from the study will have the wearable sensors removed immediately. Any data collected prior to the withdrawal will remain a part of the study, and this data will be coded.

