# 5. Statistical Analysis

## 5.1. Statistical Plan

Measurements made through clinical standard of care will be compared to the measurements recorded by the wearable sensors. Distribution checks for normality and data accuracy will be completed for each individual and for the entire study prior to all analyses. For continuous measures of physiology, 30 second epochs will be defined for each method for comparison.

Agreement and correlation of wearable biosensor measures to standard of care measures will be assessed in two ways. First, Bland–Altman plots will be created to assess agreement between each measurement system via bias and precision, which reflect the mean or average difference between two methods and the variation in these differences, respectively. Our second method consists of individual correlations between methods assessed for each person. This correlational method will supplement additional methods, and can be directly transformed to variance shared between wearable biosensor and standard of care measures, a common metric of reliability of any measure.

Formal tests of bias, precision, and correlations: While the above methods will yield useful statistics, they need to be extended to deal with the structured nature of our data. Specifically, our data are clustered, meaning that we have multiple observations within each person and multiple people in our sample, which violates standard independence assumptions inherent to many models. We propose to estimate bias and correlation/reliability using multi-level models, which yield the same statistics discussed above but account for the fact that observations taken from the same patient are more related than comparisons involving different patients.

Data will be cleaned and analyzed using IBM SPSS Statistics 20.0, unless a newer version of SPSS is available. Using repeated-measures analysis of variance (RM-ANOVA), with the study phase (pre-, during-, and post-kangaroo care) as the repeated factor, we will test differences across study phase for maternal cortisol, paternal cortisol, infant cortisol, paternal oxytocin, and paternal testosterone. We will use a two-tailed test with a 5% level of significance analysis. In addition to tracking changes over the period of kangaroo care, we will also examine within-triad correlations in cortisol for mother-father-

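### The RM-ANOVA planned for the five hormone endpoints uses only people with all three saliva samples, and no missing-sample rule offsets this; a mixed model on all available samples would serve better

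*Combined protocol and SAP*

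**What the plan says.** Section 5.1 names one method for change over the session, "Using repeated-measures analysis of variance (RM-ANOVA), with the study phase (pre-, during-, and post-kangaroo care) as the repeated factor", and applies it to "maternal cortisol, paternal cortisol, infant cortisol, paternal oxytocin, and paternal testosterone". The test level is stated once: "We will use a two-tailed test with a 5% level of significance analysis". The software is SPSS, but no procedure within it is named.

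Section 3.3 (Saliva Sample Collection) sets three samples per session: just before, half an hour in, and half an hour after the end (T1, T2, T3). On who gives them it says "Before, during, and after each KC session, saliva will be collected from the participating parent, and their infant". With one KMC and one KFC session per family, each parent gives three samples and each infant six.

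Section 4.2 lists as a ground for discontinuation being "unwilling or unable to tolerate the wearable sensors, saliva collection, or skin-to-skin session". Section 4.3 says of those who withdraw: "Any data collected prior to the withdrawal will remain a part of the study".

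No section says what happens when a saliva sample is missing. There is no deletion rule, no imputation and no expected missing rate. Section 2.2.2 names mixed-effect linear regression after its list of secondary outcomes, which includes the hormones, but ties it to between-group differences. In Section 5.1, multi-level models are proposed only for agreement between the sensors and standard-of-care monitoring.

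**The concern.** Classical RM-ANOVA with phase as a within-person factor needs a value at every phase. In the usual SPSS repeated-measures procedure, a person who lacks one sample leaves that analysis entirely. This is a property of the method, not wording in the plan, but nothing in the plan changes it.

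Two things are at stake. The first is precision: the samples that an incomplete person did give add nothing to the phase test. The second is bias. Cortisol is measured as a marker of stress, and Section 4.2 foresees losing people who do not tolerate the procedures. If those people have different cortisol courses, the complete cases are a selected group. Selection of that kind could look like a cortisol fall during kangaroo care, which would favour the study hypothesis.

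Someone who gives T1 and T2 and then withdraws illustrates the gap. Section 4.3 keeps both samples in the study, yet the named phase test cannot use them.

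**Working it through.** **The plan's own figure.** The power paragraph of Section 5.1 claims more than 99%. It cannot be reproduced, because no sample size, effect size, variance, within-person correlation or missing rate is given. It also refers to multilevel models, not RM-ANOVA. Everything below is therefore illustrative.

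**Inputs.** From the documents: three samples per person per session (Section 3.3) and a two-sided 5% level (Section 5.1). Assumed: each sample is missing with probability m = 5%, 10% or 20%, independently and completely at random; equal variances and a common within-person correlation ρ between 0.3 and 0.8.

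**Step 1: complete cases.** The share with all three samples is (1 − m)³.
- m = 5%: 0.95³ = 0.857
- m = 10%: 0.90³ = 0.729
- m = 20%: 0.80³ = 0.512

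The share of collected samples left out of the phase test is 1 − (1 − m)³/(1 − m) = 1 − (1 − m)²: 9.8%, 19.0% and 36.0%.

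**Step 2: standard error against the alternative.** The fair comparison is with a model that uses every sample obtained, since no model recovers samples never taken. For a contrast between two phases, with unit variance and per person enrolled:
- Complete cases: variance = 2(1 − ρ)/(1 − m)³.
- All available samples: add the generalised-least-squares information over every pattern of observed samples, weighting a pattern with r samples by (1 − m)^r · m^(3 − r), invert the sum, and take the variance of the contrast.

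Worked case, m = 10%, ρ = 0.5: complete cases 1.000/0.729 = 1.372; all available 1.151; SE ratio √(1.372/1.151) = 1.09.

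| m | SE ratio, ρ = 0.3 | ρ = 0.5 | ρ = 0.8 |
|---|---|---|---|
| 5% | 1.046 | 1.044 | 1.040 |
| 10% | 1.098 | 1.092 | 1.084 |
| 20% | 1.219 | 1.203 | 1.184 |

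So the complete-case SE is larger by about 4-5%, 8-10% and 18-22%.

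**Step 3: power.** With an assumed 40 people, effect size f = 0.25, ρ = 0.5 and a chi-square approximation, power with all available samples against complete cases is about 0.93 against 0.90 (5% missing), 0.91 against 0.85 (10%) and 0.85 against 0.70 (20%).

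**Step 4: direction of bias.** Suppose there is no true change, values are normal with SD 1, and half of those in the top fifth at T2 then lack T3 (10% of people). The complete-case mean at T2 is −0.5 × 0.280/0.9 = −0.156, where 0.280 is the normal density at the 80th centile. The T1 mean shifts by ρ times that. The apparent T1-to-T2 change is −0.156 × (1 − ρ): −0.11 SD at ρ = 0.3 and −0.03 SD at ρ = 0.8. A likelihood-based model on all samples is not biased here, because the missingness depends only on the observed T2 value.

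**The case against.** Several points on the other side stand.

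- **Section 4.3.** A reader might infer that RM-ANOVA breaks a promise to keep the data. It does not. Section 4.3 is a retention rule for those who withdraw, and does not say that every value enters every model. Deletion is per analysis, so the retained samples could still serve the planned hormone correlations. Section 4.3 also does not cover someone who stays in the study and misses one sample.
- **Section 4.2.** It permits discontinuation and does not forecast it. Its examples concern adhesive reactions and sensor removal, not saliva. The link from missing samples to stress is plausible but is an inference.
- **Size.** One might quote a 17% larger SE at 10% missing (1/√0.729 = 1.17). That compares complete cases with no missing data at all; only about 8-10% is due to the choice of model. One might also quote 74%, 53% and 26% complete cases from (1 − m)⁶ for the infant's six samples. Those need both sessions in one listwise model, and Section 5.1 names phase as the only repeated factor.
- **Independence.** If people stop and lose later samples, missingness clusters within persons. At a 10% per-sample rate, the complete-case share can lie anywhere from 1 − 3(0.10) = 70% (losses never coincide) to 1 − 0.10 = 90% (all three lost together). In the last case the two methods use the same data.
- **Mixed models are already named.** Section 2.2.2 could be read to cover the hormones. Its scope is unclear, and Section 5.1 names a different method for the phase test, so this calls for alignment but does not close the gap.

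**Conclusion.** The point holds as a weakness in the method chosen for five secondary endpoints. RM-ANOVA is by default a complete-case analysis, and nothing in the plan offsets this. Missing saliva samples are foreseeable from the plan's own discontinuation criteria.

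The loss of precision is modest at low missing rates and material at 20%. The sizes rest on assumed rates, independent missingness and compound symmetry; the documents supply none of these. Bias is possible, but neither its presence nor its size can be established from the documents.

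A reader might go further and say that the plan states it will drop incomplete participants, or that Sections 4.3 and 5.1 contradict each other. Neither is supported. The deletion is a default consequence of the named method, with the SPSS procedure unspecified, and retaining data is compatible with not using them in one model.

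**What to change.** In Section 5.1, replace RM-ANOVA for each of the five endpoints with a linear mixed model (SPSS MIXED, REML). Use all available samples, phase as a fixed effect, and a within-person covariance structure or random intercept, and keep the two-sided 5% level.

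In the infant cortisol model only, add session type (KMC or KFC), its interaction with phase, and session order. Each parent is sampled at one session type, so a session-type effect cannot be estimated in the maternal and paternal models.

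State that samples obtained before withdrawal enter these models, report the number of missing samples by phase with reasons, and say in Section 2.2.2 whether its mixed-effect regression is this same analysis.

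The cost is a change of wording; data, software and test level stay the same. The downside is reliance on missing at random. That is generally weaker than what complete-case analysis needs, but it does not remove bias if a sample is missing because of a stress response that was never observed.

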#### Kangaroo Care (KC) Intervention:

After enrollment, families will be scheduled to participate in two sessions of KC. The goal will be to schedule the KC sessions over two sequential days and at approximately the same time of day (i.e. morning, afternoon, or evening). However, if this is not possible given the parents' schedules, the sessions will be scheduled for the days and time of day that participating parents are able to visit their infant in the NICU. Each session will include two hours of continuous KC, with one day focused on Kangaroo Mother Care (KMC) and the other on Kangaroo Father Care (KFC), in a randomized order. These sessions will include continuous skin-to-skin holding of the infant by the parent, per standard of care protocol.

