infants in the same family, as well as correlations between infant cortisol and father testosterone/oxytocin, and maternal cortisol and father testosterone-oxytocin.

Statistical Power: The large amount of within-person data provides incredibly high statistical power for all planned and many secondary data analyses, allowing this data set to answer all proposed questions. Previous work on power in multilevel models found greater than 99% power to detect associations with the planned observations suggested here within comparable nested designs.

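### Infant cortisol is sampled at three phases in each of two randomised-order sessions, but the stated RM-ANOVA has phase as its only repeated factor and does not say how the two sessions enter

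*Combined protocol and SAP*

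**What the plan says.** Under Kangaroo Care (KC) Intervention in section 3.3, "families will be scheduled to participate in two sessions of KC", "with one day focused on Kangaroo Mother Care (KMC) and the other on Kangaroo Father Care (KFC), in a randomized order". Under Saliva Sample Collection in the same section, "Before, during, and after each KC session, saliva will be collected from the participating parent, and their infant". There are three sampling times per session: just before holding starts, half an hour into it, and half an hour after it ends.

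Section 5.1 then states a single repeated-measures ANOVA for maternal cortisol, paternal cortisol, infant cortisol, paternal oxytocin and paternal testosterone, "with the study phase (pre-, during-, and post-kangaroo care) as the repeated factor". On the error rate it adds: "We will use a two-tailed test with a 5% level of significance analysis". It names no session, holding-parent, order or period term for any of the five series.

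Two other places touch on dependence within a person. Section 5.1 recognises that its data are clustered, and the remedy it gives is "We propose to estimate bias and correlation/reliability using multi-level models", in the part on agreement between the wearable sensors and standard monitoring. Section 2.2.2, which lists infant cortisol reactivity among the secondary outcomes, closes with a general sentence naming two-sample t tests and mixed-effect linear regression for between-group differences.

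**The concern.** One model form is applied to series with two different structures. Each parent contributes three values from one session, which is what a three-level phase factor expects. Each infant contributes six values in a 3 x 2 layout, phase by holding parent. To fit six values into a three-level factor the analyst must average the sessions, run them separately, or enter each session as its own row. The plan does not choose.

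Two things are at stake. First, the main hypothesis in section 2.1 concerns father holding, and each infant is held by both parents in randomised order. The written model has no term for that comparison in infant cortisol, the only hormone series measured in the infant. Second, one of the permitted routes can make the phase effect look more certain than it is. Leaving the choice until the data are seen also leaves room to choose among results.

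**Working it through.** **The plan's own figure.** The only computed design figure is the power statement in section 5.1, "greater than 99% power to detect associations with the planned observations suggested here within comparable nested designs". It cannot be reproduced, because no sample size, effect size, standard deviation or within-infant correlation is given. It therefore does not help to settle this point.

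**Counts from the documents.**
- Infant: 2 sessions x 3 samples = 6.
- Each parent: 1 session x 3 samples = 3.
- Levels of the stated repeated factor: 3.

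**Ways to fit six infant values to a three-level phase factor.**
1. *Average the two sessions within phase.* The infant is the unit. The simulated false-positive rate stays close to the nominal 5%, but the comparison of holding parents is averaged away.
2. *Analyse each session separately.* Each test also stays close to 5%. There are then two phase tests where one is stated, and neither compares the sessions directly.
3. *Stack the sessions as separate subjects.* The level depends on a correlation, as follows.

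**Stacked phase test.** Let rho be the correlation, within an infant and between the two sessions, of the phase contrasts. The true variance of the phase means is (1 + rho) times what the stacked test assumes, so standard errors are too small by a factor of sqrt(1 + rho). For a three-level factor the test has 2 numerator degrees of freedom, and the 5% point of chi-squared on 2 df is 5.991. In large samples:

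false-positive rate = P(chi-squared on 2 df > 5.991/(1 + rho)) = exp(-2.996/(1 + rho)).

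For example, rho = 0.3 gives exp(-2.996/1.3) = exp(-2.305) = 0.0998. The values of rho and the numbers of infants are assumptions; simulation used 20,000 data sets per setting.

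| rho (assumed) | SE too small by | Formula | Simulated, 20 infants |
|---|---|---|---|
| 0 | 1.00 | 5.0% | 4.9% |
| 0.3 | 1.14 | 10.0% | 9.9% |
| 0.5 | 1.22 | 13.6% | 13.9% |
| 0.58 | 1.26 | 15.0% | not run |
| 0.8 | 1.34 | 18.9% | 20.1% |
| 1.0 | 1.41 | 22.4% | 23.0% |

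Results with 10, 40 and 80 infants were similar. A slightly negative rho of -0.2 would make the test conservative (2.4%).

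**What drives it.** A stable high or low cortisol level in an infant does no harm, because it cancels in the within-row contrasts. With rho = 0, 30 infants, and an infant-level variance of 0, 1 or 9 times the residual, the rate was 4.9%, 5.1% and 4.9%. Only a phase response that repeats across sessions inflates the error.

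**Infant as the unit.** With sessions averaged, or one session analysed alone, the simulated rate was 4.6% to 5.5% over all settings.

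**Stacking with session as a between-subject factor.** Here the mother-versus-father tests err the other way. With an infant-level variance equal to the within-session variance, the session main effect rejects at most 0.1% of the time. The session-by-phase test rejects about 1.5% at rho = 0.3 and 0.3% at rho = 0.5. That is a loss of power, not false positives.

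**Check on the remedy.** A mixed model with only infant and infant-by-phase random effects would not be enough. Let s be the infant-by-session variance and e the residual variance. That model pools the two into about e + s, whereas the holding-parent contrast really varies as e + 3s. The variance ratio is (e + 3s)/(e + s). Taking e = 0.7 (assumed):
- s = 0.25: 1.45/0.95 = 1.53; the 1.96 cut-off acts as 1.96/1.24 = 1.59, about 11%.
- s = 0.5: 2.2/1.2 = 1.83; 1.96/1.35 = 1.45, about 15%.
- s = 1.0: 3.7/1.7 = 2.18; 1.96/1.48 = 1.33, about 18%.

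An infant-by-session effect is therefore needed.

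**The case against.** The strongest reply is that no error is written down. Section 5.1 never says sessions will be stacked. One phase analysis per session is a natural reading: it leaves the stated model unchanged and mirrors the separate maternal and paternal series. It also keeps 5%, as averaging does. This stands. A reader might infer that the plan counts each infant twice and so doubles or triples the false-positive rate, but the documents do not support that. Stacking is only one of the readings left open, counting twice does not by itself inflate the phase test, and doubling or tripling needs rho of about 0.30 or 0.58, values found nowhere in the documents.

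A second reply is that the plan already provides for clustering and names mixed models. This stands only in part. The multi-level models in section 5.1 are proposed for device bias and reliability, and the hormone test is specified separately as an RM-ANOVA. The closing sentence of section 2.2.2 may belong mainly to the questionnaires, and it names no infant unit, random effect or session factor. A two-sample t test of infant values by holding parent would itself treat one infant as two.

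Third, infant cortisol is one secondary series. That limits the weight of the point but does not remove the gap.

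**Conclusion.** The point holds as a mismatch between design and model, confined to infant cortisol. The stated RM-ANOVA suits the four parent series. For the infant's 3 x 2 layout it leaves the analysis undefined, and none of the routes that fit it as written gives both a sound phase test and a proper within-infant test of father against mother holding.

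The size is conditional. With averaging or separate analyses the level is about 5% and the cost is the missing direct comparison. With stacking, the phase test's level runs from 5% at rho = 0 to about 22% at rho = 1, with about 10% at 0.3 and 14% at 0.5. These figures assume normal data, complete pairs of sessions and a non-negative rho. The lack of a direct comparison under averaging or separate analyses needs no such assumption.

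**What to change.** In section 5.1, specify for infant cortisol a two-way within-infant analysis: phase (3 levels), holding parent (2 levels) and their interaction, plus session order/period, with the infant as the unit. Either of two forms will do:
- a two-factor RM-ANOVA with separate within-infant error terms for phase, holding parent and their interaction, and order as a between-infant factor (its interaction with holding parent then carries the period effect); or
- a mixed model with random effects for infant, infant-by-phase and infant-by-session.

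The infant-by-session term should not be dropped, for the reason shown in the check on the remedy. State which term answers which question: phase for change over a session, holding parent and its interaction with phase for father against mother. Keep the three-level phase model for the parent series.

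The cost is a sentence or two in the plan and a slightly more complex model for one secondary outcome. The data and software stay the same.

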# 2.2. Outcome Measures

## 2.2.1. Primary Outcome

Primary outcome measures include heart rate (HR) and oxygen saturation (SpO2) as indicators of cardiorespiratory stability in infants before, during, and after KC and HR and HR variability (HRV) as indicators of physiologic stress in NICU parents during and after periods of KC. All of these outcomes will be measured using wearable, wireless biosensors.

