#### **Physiologic Recording:**

*Infant*: Prior to the first scheduled KC session, two wearable, wireless biosensors will be placed on the infant to continuously capture physiology measures including electrocardiogram (ECG), heart rate (HR), oxygen saturation (SpO2), body temperature, respiratory rate, movement, systolic blood pressure (BP-S), and others for the duration of the study. One device will be placed on the infant's chest or back. A second device will be placed peripherally, on the infant's leg, foot, arm, or hand. The devices are encapsulated in a medical-grade silicone and will be adhered to the infant's skin using a medical-grade adhesive, similar to the adhesives standardly used in the NICU. The biosensors will be left in place for up to 48 hours, but will be checked by study staff at least once every 24 hours to ensure skin integrity and signal quality. The adhesives will be changed between uses.

**Parent:** The same type of wearable, wireless biosensor will also be used to record 4 hours of continuous physiology including ECG, HR, temperature, movement, SpO2, and others in the infant's parents. The biosensor will be placed on the parent's chest 1 hour before the start of a scheduled KC session and worn for 1 hour preceding the scheduled KC session, during the 2-hour KC session, and for 1 hour after the completion of the KC session. The biosensor will be worn by the parents for approximately 4 hours in total.

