#### Standard of Care Data Collection:

In all patients in rooms where data from standard of care monitoring is recorded on the BedMaster system, this data will be used for comparison to data captured using the wearable sensors. In participants in rooms where this system is not available, the MediCollector system will be used to capture background data during the approximately 48-hour study.

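### Section 5.1 states no test of a kangaroo care effect on any of the four primary outcomes, and no stated model uses the randomised KFC/KMC sessions

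*Combined protocol and SAP*

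**What the plan says.** **Hypothesis and primary outcomes.** Section 2.1 expects KFC to benefit acute physiologic and long-term behavioural outcomes; it names no comparator. Section 2.2.1 reads: "Primary outcome measures include heart rate (HR) and oxygen saturation (SpO2) as indicators of cardiorespiratory stability in infants before, during, and after KC". For parents it lists "HR and HR variability (HRV) as indicators of physiologic stress in NICU parents during and after periods of KC".

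**Design.** Section 3.3 schedules two sessions per family, "with one day focused on Kangaroo Mother Care (KMC) and the other on Kangaroo Father Care (KFC), in a randomized order". The parent sensor is "worn for 1 hour preceding the scheduled KC session, during the 2-hour KC session, and for 1 hour after the completion" of the session, so a pre-session hour is recorded. On saliva: "Before, during, and after each KC session, saliva will be collected from the participating parent, and their infant". Each infant is therefore sampled in two sessions and each parent in one.

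**Analysis.** Section 5.1 contains four things:
- Wearable versus standard-of-care agreement, by Bland–Altman plots and per-person correlations, extended to clustered data: "We propose to estimate bias and correlation/reliability using multi-level models".
- A repeated-measures ANOVA with study phase "as the repeated factor, we will test differences across study phase for maternal cortisol, paternal cortisol, infant cortisol, paternal oxytocin, and paternal testosterone", two-sided at 5%.
- Correlations between hormones within families.
- A statement that power exceeds 99% and that the data can answer every question proposed.

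The standard-of-care reference is described under Standard of Care Data Collection: "In all patients in rooms where data from standard of care monitoring is recorded on the BedMaster system", with a second capture system for other rooms. No reference monitor for parents is described.

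Outside Section 5, the paragraph on secondary outcomes (2.2.2) ends with two-sample t tests and mixed-effect regressions for differences between groups, adjusted for age, education, socio-economic status, stress and depression. It does not say what the groups are.

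**The concern.** A sensor can agree perfectly with the bedside monitor whether or not skin-to-skin holding changes the infant's heart rate. Agreement is a different question from the one in Section 2.1, and it is the only question Section 5.1 puts to continuous physiology. If the plan is followed literally, the report has no result on its main hypothesis for its primary outcomes. If it is not, the contrast, the phase summary, the baseline and the handling of two sessions per infant are all open choices, and unless the plan is amended first they will be made with the data in view.

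The randomisation is also left idle. Session order is the only randomised element of the study, and no stated analysis names it.

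**Working it through.** **1. The plan's own figure.** The power of more than 99% cannot be reproduced: no number of families, effect size, SD, intraclass correlation or target contrast is given. The check is therefore a mapping of outcomes to analyses.

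**2. Mapping.**

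| Primary outcome | Sensor agreement | Phase test | KFC vs KMC |
|---|---|---|---|
| Infant HR | yes | none | none |
| Infant SpO2 | yes | none | none |
| Parent HR | no reference monitor described | none | none |
| Parent HRV | no reference monitor described | none | none |

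Section 5.1 names neither HR nor SpO2; it speaks of continuous measures of physiology. That these include infant HR and SpO2 follows from the bedside-monitor comparison in Section 3.3. Outcomes with an effect test: 0 of 4. Models naming holder, period or sequence: 0.

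**3. Hormones.** The ANOVA list is closed: five measures of three hormones (cortisol in mother, father and infant; paternal oxytocin; paternal testosterone), all secondary in 2.2.2. A phase test matches how 2.2.2 defines them. The gap is infant cortisol: two sessions of three samples give six values per infant, and the plan does not say how the two sessions enter.

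**4. Section 2.2.2.** The sentence on group differences follows the questionnaire scores and adjusts for parental characteristics, so it most likely concerns the questionnaires. Every family is scheduled for both sessions, so the groups are not evident.

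**5. What the randomised design could estimate.** For each infant let D = (during − pre, KFC session) − (during − pre, KMC session). Let τ be the KFC−KMC difference and δ the first-minus-second-session difference in the change.
- KFC first: E(D) = τ + δ. KMC first: E(D) = τ − δ.
- Mean of the two sequence means: [(τ + δ) + (τ − δ)]/2 = τ. The period effect drops out (N − 2 df).
- If the first session carries over into the change in the second by λF after KFC and λM after KMC, the estimate becomes τ + (λM − λF)/2. Equal carryover cancels; differential carryover does not, so its absence must be stated as an assumption.

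**6. Illustration only (assumed inputs).** Infant, session and infant-by-phase effects cancel in D, leaving four residuals: SD(D) = 2σ. Take a difference of 0.5 and a two-sided 5% test.
- σ = 0.5 gives SD(D) = 1.0 and power 56% / 75% / 87% at N = 20 / 30 / 40 infants.
- σ = 0.9 gives SD(D) = 1.8 and power 22% / 31% / 40%.
- With σ = 0.5, N = 30 and δ = 0.5 or 1.0, a plain paired t test has power 67% or 44%; the period-adjusted version stays at 75%.
- Families needed, n = ((1.960 + z)/d)², with d the standardised paired difference: at d = 0.5, (2.802/0.5)² = 31.4, so 32 for 80% power; (4.286/0.5)² = 73.5, so 74 for 99%. At d = 0.2 the figures are 197 and 460.

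More readings per person do not lift this limit. With 20 families, a difference of 0.5 and a family-level SD of 1, power cannot exceed Φ(0.5 × √20 − 1.960) = Φ(0.276) = 60.9%, however many readings are taken.

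**The case against.** The strongest reply is that KFC versus KMC was never promised. Section 2.1 names no comparator, and the order may be randomised only to counterbalance. That stands: a reader might infer that the randomised contrast must be the primary analysis, and the documents do not support this. They support asking what the randomisation is for. The reply does not touch the main gap, because the phase test for all four primary outcomes is missing either way.

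A second reply is that 2.2.2 already supplies mixed models. It does so under secondary outcomes, with undefined groups.

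Four other inferences would go too far:
- *That the hormone ANOVA is the wrong analysis.* It fits 2.2.2 and should stay.
- *That phase changes cannot be separated from elapsed time at all.* That holds only with one value per phase and unrestricted phase effects. The parents' four continuous hours allow separation if drift is assumed linear and, for a during-versus-(pre and post) contrast, if no effect persists. Nonlinear drift stays confounded, so caution is right but impossibility is not shown.
- *That the two-sample t test would produce false positives.* The plan does not assign it to the infants' two sessions. If it were so used, with positively correlated sessions, the cost would be lost power.
- *That the primary analysis must be chosen after seeing the data.* The infant phases and the 5% two-sided level are already fixed, and the plan can be amended before analysis.

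**Conclusion.** The point holds and should be fixed before analysis. From the documents alone, 0 of 4 primary outcomes has a stated test of a kangaroo care effect, parent HR and HRV have no stated analysis of any kind, and 0 models include holder or period. This is more than missing detail, because the one analysis given for continuous physiology answers a different question. It also contradicts the claim under Statistical Power that the data set can answer every question proposed.

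The unused KFC/KMC order, the handling of infant cortisol and the undefined groups in 2.2.2 are gaps to be clarified, not proof of a wrong analysis. The counts need no assumptions. The power figures rest wholly on assumed sample sizes, SDs and effects and say nothing about this trial's actual power.

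**What to change.** 1. **Phase analysis of the primary outcomes (5.1).** Add a pre/during/post analysis for infant HR and SpO2 in KFC sessions, and for parent HR and HRV in each parent's own session. Use one predefined summary per phase per session. State the infant's pre and post windows; one-hour windows are given only for parents. Use the parents' recorded pre-session hour as baseline; 2.2.1 names only the during and after periods for them.
2. **Randomised contrast.** For infant HR and SpO2, and for infant cortisol alongside the phase ANOVA, estimate the mean of the two sequence-specific means of D on N − 2 df, and repeat for post minus pre. State the assumption of no differential carryover. Say whether the order is randomised for comparison or for counterbalancing, and label the contrast primary or supportive accordingly.
3. **Hormones.** Keep the repeated-measures ANOVA. State that infant cortisol enters with session (KFC/KMC) as a second within-infant factor.
4. **Reporting.** Describe within-session phase changes as uncontrolled, since separating them from elapsed time needs assumptions about drift.
5. **Section 2.2.2.** Define the groups and the outcomes that the sentence covers. Do not use two-sample t tests to compare the same infants' two sessions.

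**Cost.** SAP wording and slightly more analysis; no new data, since session order and phase are inherent to the procedures. Conclusions for parents become more modest, and the paired contrast uses only infants with both sessions.
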